9.5.2 Appropriateness of Measurements

All clinical assessments are standard measurements commonly used in studies of soft tissue sarcomas.

The safety assessments to be performed in this study, including hematology analyses, blood chemistry tests, urinalysis, radiologic studies, and assessment of AEs, are standard evaluations to ensure subject safety.

9.5.3 Reporting of Serious Adverse Events, Pregnancy, and Events Associated with Special Situations

9.5.3.1 Reporting of Serious Adverse Events

All SERIOUS ADVERSE EVENTS, regardless of their relationship to study treatment, must be reported on a completed SAE form by email or fax as soon as possible but no later than 24 hours from when the investigator becomes aware of the event. Deaths and life-threatening events should be reported immediately by telephone. The immediate report should be followed up within 24 hours by emailing or faxing the completed SAE form.

Serious adverse events, regardless of causality assessment, must be collected through the last visit in the Treatment Phase, and for 28 days after the subject's last dose. All SAEs must be followed to resolution or, if resolution is unlikely, to stabilization. Any SAE judged by the investigator to be related to the study treatment or any protocol-required procedure should be reported to the sponsor regardless of the length of time that has passed since study completion.

The detailed contact information for reporting of SAEs is provided in the Investigator Study File.

For urgent safety issues, please ensure all appropriate medical care is administered to the subject and contact the appropriate study team member listed in the Investigator Study File.

It is very important that the SAE report form be filled out as completely as possible at the time of the initial report. This includes the investigator's assessment of causality.

Any follow-up information received on SAEs should be forwarded within 24 hours of its receipt. If the follow-up information changes the investigator's assessment of causality, this should also be noted on the follow-up SAE form.

Preliminary SAE reports should be followed as soon as possible by detailed descriptions including copies of hospital case reports, autopsy reports, and other documents requested by the sponsor.

The investigator must notify his/her IRB/IEC of the occurrence of the SAE in writing, if required by their institution. A copy of this communication must be forwarded to the sponsor to be filed in the sponsor's Trial Master File.

9.5.3.2 Reporting of Pregnancy and Exposure to Study Drug Through Breastfeeding

Any pregnancy in which the estimated date of conception is either before the last visit or within 28 days of last study treatment, or any exposure to study drug through breastfeeding during study treatment or within 28 days of last study treatment, must be reported.

If an adverse outcome of a pregnancy is suspected to be related to study drug exposure, this should be reported regardless of the length of time that has passed since the exposure to study treatment.

A congenital anomaly, death during perinatal period, an induced abortion, or a spontaneous abortion are considered to be an SAE and should be reported in the same time frame and in the same format as all other SAEs (see Reporting of Serious Adverse Events [Section 9.5.3.1]).

Pregnancies or exposure to study drug through breastfeeding must be reported by fax or email as soon as possible but no later than 1 business day from the date the investigator becomes aware of the pregnancy. The contact information for the reporting of pregnancies and exposure to study drug through breastfeeding is provided in the Investigator Study File. The Pregnancy Report Form must be used for reporting. All pregnancies must be followed to outcome. The outcome of the pregnancy must be reported as soon as possible but no later than 1 business day from the date the investigator becomes aware of the outcome.

A subject who becomes pregnant must be withdrawn from the study. The investigator should confirm whether they agree to follow-up assessments (including survival follow-up) or whether the subject wishes to withdraw consent. If a subject withdraws consent, the date should be documented in the source documents.

9.5.3.3 Reporting of Events Associated with Special Situations

9.5.3.3.1 REPORTING OF ADVERSE EVENTS ASSOCIATED WITH STUDY DRUG OVERDOSE, MISUSE, ABUSE, OR MEDICATION ERROR

Adverse events associated with study drug overdose, misuse, abuse, and medication error refer to AEs associated with uses of the study drug outside of that specified by the protocol. Overdose, misuse, abuse, and medication error are defined as follows:

Overdose Accidental or intentional use of the study drug in an amount higher than the protocol-defined dose.

Misuse Intentional and inappropriate use of study drug not in accordance with the protocol.

Abuse	Sporadic or persistent intentional excessive use of study drug accompanied by harmful physical or psychological effects
Medication error	Any unintentional event that causes or leads to inappropriate study drug use or subject harm while the study drug is in the control of site personnel or the subject.
All AEs associated with overdose, misuse, abuse, or medication error should be captured on the Adverse Event CRF and also reported using the procedures detailed in Reporting of Serious Adverse Events (Section 9.5.3.1) even if the AEs do not meet serious criteria. Abuse is always to be captured as an AE. If the AE associated with an overdose, misuse, abuse, or medication error does not meet serious criteria, it must still be reported using the SAE form and in an expedited manner but should be noted as nonserious on the SAE form and the Adverse Event CRF.	

9.5.3.4 Expedited Reporting

The sponsor must inform investigators and regulatory authorities of reportable events, in compliance with applicable regulatory requirements, on an expedited basis (ie, within specific time frames). For this reason, it is imperative that sites provide complete SAE information in the manner described above.

9.5.3.5 Regulatory Reporting of Adverse Events

Adverse events will be reported by the sponsor or a third party acting on behalf of the sponsor to regulatory authorities in compliance with local and regional law and established guidance. The format of these reports will be dictated by the local and regional requirements.

All studies that are conducted within any European country will comply with European Good Clinical Practice Directive 2005/28/EC and Clinical Trial Directive 2001/20/EC. All suspected unexpected serious adverse reactions (SUSARs) will be reported, as required, to the competent authorities of all involved European member states.

9.5.4 Completion/Discontinuation of Subjects

A subject may elect to discontinue the study at any time for any reason. All subjects who discontinue the study are to complete the study's discontinuation procedures indicated in the Schedule of Procedures/Assessments ([Table 13](#) and [Table 14](#)).

The investigator will promptly explain to the subject involved that the study will be discontinued for that subject and provide appropriate medical treatment and other necessary measures for the subject. A subject who has ceased to return for visits will be followed up by mail, phone, or other means to gather information such as the reason for failure to return, the status of treatment compliance, the presence or absence of AEs, and clinical courses of signs and symptoms.

Subjects who discontinue from the study will be discontinued for 1 of these primary reasons: AE(s), lost to follow-up, subject choice, inadequate therapeutic effect, progression of disease, withdrawal of consent, pregnancy, study terminated by sponsor, or other. Study disposition information will be collected on the Subject Disposition CRF.

A subject removed from the study for any reason may be replaced.

9.5.5 Abuse or Diversion of Study Drug

Not applicable.

9.6 Data Quality Assurance

This study will be organized, performed, and reported in compliance with the protocol, SOPs, working practice documents, and applicable regulations and guidelines. Site audits will be made periodically by the sponsor's or the CRO's qualified compliance auditing team, which is an independent function from the study team responsible for conduct of the study.

9.6.1 Data Collection

Data required by the protocol will be collected on the CRFs and entered into a validated data management system that is compliant with all regulatory requirements. As defined by ICH guidelines, the CRF is a printed, optical, or electronic document designed to record all of the protocol-required information to be reported to the sponsor on each study subject.

Data collection on the CRF must follow the instructions described in the CRF Completion Guidelines (CCGs). The investigator has ultimate responsibility for the collection and reporting of all clinical data entered on the CRF. The investigator or designee as identified on Form FDA 1572 must sign the completed CRF to attest to its accuracy, authenticity, and completeness.

Completed, original CRFs are the sole property of Eisai and should not be made available in any form to third parties without written permission from Eisai, except for authorized representatives of Eisai or appropriate regulatory authorities.

9.6.2 Clinical Data Management

All software applications used in the collection of data will be properly validated following standard computer system validation that is compliant with all regulatory requirements. All data, both CRF and external data (eg, laboratory data), will be entered into a clinical system.

9.7 Statistical Methods

All statistical analyses will be performed by the sponsor or designee after the study is completed and the database is locked. Statistical analyses will be performed using SAS software or other validated statistical software as required. Details of the statistical analyses will be included in a separate statistical analysis plan (SAP).

9.7.1 Statistical and Analytical Plans

The statistical analyses of study data are described in this section. Further details of the analytical plan will be provided in the SAP, which will be finalized before database lock.

9.7.1.1 Study Endpoints

9.7.1.1.1 PRIMARY ENDPOINTS

The primary endpoints of the study are:

- Phase 1: The MTD/RP2D of eribulin mesilate in combination with irinotecan hydrochloride in pediatric subjects with relapsed/refractory solid tumors, excluding CNS tumors. Note: Subjects <12 months will not contribute to the determination of MTD/RP2D and data is for descriptive purposes only.
- Phase 2: Objective response rate (ORR): defined as the proportion of subjects achieving a best overall response of confirmed partial or complete response, as determined by investigator assessment.

9.7.1.1.2 SECONDARY ENDPOINTS

The secondary endpoints of the study are:

Phase 1 & 2:

- Safety and tolerability: adverse events (AEs), serious adverse events, clinical laboratory values, ECG parameters, vital sign measurements and physical examinations.
- The pharmacokinetic profile of eribulin, irinotecan and its active metabolite.

Phase 2:

- Progression-free survival (PFS): defined as the time from the first dose date to the date of disease progression as determined by investigator assessment or death.
- The Clinical Benefit Rate (CBR): defined as the proportion of subjects with best overall response (BOR) of CR, PR or durable SD based on RECIST 1.1 (durable SD is defined as SD with duration of >11 weeks).

9.7.1.2 Definitions of Analysis Sets

Full Analysis Set (FAS) will consist of subjects who receive at least 1 dose of either study drug.

Safety Analysis Set will consist of subjects who receive at least 1 dose of either study drug.

Pharmacokinetic Analysis Set (PAS) will include subjects who have documented dosing history and at least one post-dosing quantifiable drug concentration.

Dose Evaluable Set (DES) for Phase 1 will consist of all subjects who completed Cycle 1 treatment and were evaluated for DLT, and those who discontinued during Cycle 1 due to DLT. DES will be used for evaluation of each dose level for dose-escalation and for determination of MTD.

9.7.1.3 Subject Disposition

The number and percentage of subjects who discontinue the study treatment will be tabulated, along with the primary reasons for discontinuation.

9.7.1.4 Demographic and Other Baseline Characteristics

Demographic and other baseline characteristics data will be summarized descriptively. Data to be tabulated will include data such as sex, age, and race as well as weight and disease-specific status and medical history.

9.7.1.5 Prior and Concomitant Therapy

All investigator terms for medications recorded in the CRF will be coded to an 11-digit code using the World Health Organization Drug Dictionary (WHO DD) 2017 or current. The number (percentage) of subjects who took prior and concomitant medications will be summarized by dose level, Anatomical Therapeutic Chemical (ATC) class (ie, anatomical class, therapeutic class), and WHO DD preferred term. Prior medications will be defined as medications that stopped before the first dose of study drug. Concomitant medications will be defined as medications that (1) started before the first dose of study drug and were continuing at the time of the first dose of study drug, or (2) started on or after the date of the first dose of study drug up to 30 days after the subject's last dose. All medications will be presented in subject data listings.

9.7.1.6 Efficacy Analyses

The primary efficacy analyses will be performed at the time of data cutoff, ie, when all subjects have discontinued the treatment or completed at least 6 months of treatment.

ORR, PFS, and CBR will be summarized descriptively on the FAS. Endpoints related to tumor assessments will be based on investigator assessments. Collect and hold of tumor scans will enable a possibility to confirm responses in case independent review is required.

9.7.1.6.1 PRIMARY EFFICACY ANALYSIS

ORR will be estimated and summarized for each histology type. A Simon two-stage design will be used within each histology type. The following hypothesis will be tested at a one-sided 5% significance level:

$$H_0: p \leq 30\% \quad \text{Vs} \quad H_a: p \geq 55\%.$$

The first stage will enroll 9 subjects. A futility analysis will be performed when the data for the 9 subjects is available. If there are 2 or less responders (CR or PR) among the 9 subjects, the enrollment in this histology type will be stopped. If there are 3 or more responders, the enrollment will continue to the second stage to approximately 25 subjects. If there are 12 or more responders out of 25 subjects, the null hypothesis will be rejected. For final review, collect and hold of tumor scans will enable the final report to confirm responses by potential independent radiologic review.

In addition, ORR along with respective confidence interval will be provided by histology. Duration of response (DOR) will be calculated for responders and summarized descriptively. DOR is defined as the time from the first date of documented PR or CR to the date of disease progression or date of death (whichever occurs first).

9.7.1.6.2 SECONDARY EFFICACY ANALYSES

PFS will be analyzed by Kaplan-Meier methodology and median PFS with 90% confidence interval will be presented. Clinical benefit rate (CBR) defined as the proportion of subjects with best overall response (BOR) of CR, PR or durable SD based on RECIST 1.1, will be summarized by descriptive statistics for the FAS. Durable SD is defined as SD with duration of more than 11 weeks.

9.7.1.7 Pharmacokinetic, Pharmacodynamic, Pharmacogenomic, and Other Biomarker Analyses

9.7.1.7.1 PHARMACOKINETIC ANALYSES

Plasma concentrations of eribulin, irinotecan and its active metabolite SN-38 will be tabulated and summarized by dose level, day and time. For Phase 1, PK parameters for eribulin, irinotecan and SN-38 will be derived from plasma concentrations by noncompartmental analysis using actual times. Minimally, the following PK parameters will be calculated: maximum observed plasma concentration (C_{max}), time of maximum observed concentration following drug administration (t_{max}), area under the concentration-time curve (AUC).

In Phase 1 the PK of both drugs (eribulin and irinotecan) will be assessed on C1D1 and in Phase 2 eribulin will be assessed on C1D1 and C1D8. The Phase 2 PK data will be assessed using a PopPK approach, pooled with Phase 1 data. A population PK model for eribulin will be developed using non-linear mixed effect modelling. The model will be parameterized in terms of clearance and volume of distribution parameters.

9.7.1.7.2 PHARMACOKINETIC AND PHARMACODYNAMIC ANALYSES

Exploratory/graphical analysis will be conducted for PK/PD evaluations, ie, dose and/or exposure effect relationships will be explored for the effects of eribulin mesilate on tumor responses as determined by RECIST 1.1 (CR, PR and SD), PFS and ORR, as well as AEs/dose reductions, and may be followed by model-based analysis. In addition, the effects of eribulin

mesylate administration on absolute neutrophil count (ANC) may be evaluated using a semi-physiological model for hematological toxicity.

Further details will be documented separately in a population analysis plan (PAP).

9.7.1.8 Safety Analyses

The primary endpoint for Phase 1, i.e., the incidence of DLTs will be summarized by dose level for the DES using frequency and percentage.

Additionally, toxicity in Phase 2 for the Safety Analysis Set will be monitored on an ongoing basis. If the number of AEs that would have qualified as DLTs on the Phase 1 portion exceeds 1/3, a meeting with the investigators will be convened to determine if the dose should be lowered. The rule of one-third (1/3) will be applied to the number of subjects in an increment of 3 subjects at the same dose level (eg, 3, 6, 9 subjects). Likewise, if ongoing moderate toxicities develop into “intolerable Grade 2” events, the recommended Phase 2 dose may also be re-evaluated in consultation with the protocol investigators.

All evaluation of safety other than the Phase 1 primary objective in DLT evaluation will be performed on the Safety Analysis Set. Safety data that will be evaluated include adverse events, clinical laboratory results, ECG, and vital signs.

Descriptive summary statistics (mean, standard deviation, median, minimum, maximum) of clinical laboratory test results, vital signs measurements, ECG parameters, and changes from baseline will be presented.

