1. Grade 3 or 4 non-hematological toxicities related to study drug **except for:**
 - inadequately treated nausea and/or vomiting,
 - Grade 3 liver enzyme elevation (including ALT/AST),
 - Grade 3 fever or Grade 3 infection,
 - Grade 3 hypophosphatemia, hypokalemia, hypocalcemia or hypomagnesemia responsive to oral supplementation
2. Grade 3 or above diarrhea despite adequate treatment
3. Non-hematological toxicity that causes a delay of ≥ 14 days between treatment cycles
4. Day 8 dose omission or interruption for more than 2 weeks due to non-recovery of any toxicity related to the study drug
5. For subjects <12 months (at the time of DLT), any \geq Grade 2 drug-related non-hematological toxicity
6. **DLT exception:** Allergic reactions that lead to discontinuation of study drug during Cycle 1

Accrual will be suspended when a cohort of 3 or 6 has enrolled with pending toxicity data or when the MTD/RP2D for the combination has been met. If, following de-escalation from dose level 0 (to dose level-1), 2 DLTs are observed, that dose and schedule will be declared too toxic for further evaluation. For subjects <12 months, if following de-escalation from dose level -1 (to dose level -2 in Schedule A), 2 DLTs are observed, that dose and schedule will be declared too toxic for further evaluation. Up to 36 pediatric subjects (18 subjects per schedule) who meet all the inclusion criteria and none of the exclusion criteria, will be enrolled in Phase 1. The sample size does not include subjects <12 months.

[figure not shown]
MTDs will be obtained for both Schedule A and Schedule B and the most appropriate schedule will be taken forward to Phase 2 and will represent the RP2D (See Section 9.4.1 for details on schedule selection).

Phase 2: Will evaluate the safety and efficacy of eribulin mesilate in combination with irinotecan hydrochloride in pediatric subjects with relapsed/refractory RMS, NRSTS and EWS, using the combination dose and schedule determined in Phase 1. As per protocol amendment #5, following review of the data from the Phase 1 portion of the study, Schedule A Dose Level 1 - eribulin (dose 1.4 mg/m^2) Day 1 and Day 8 and irinotecan (dose 40 mg/m^2) Days 1-5, was selected as the dose and schedule to take forward into Phase 2 (RP2D). As per Amendment 6, subjects aged >6 months and

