Plasma concentrations of eribulin, irinotecan and its active metabolite SN-38 will be tabulated and summarized by dose level, day and time. In Phase 1, PK parameters for eribulin, irinotecan and SN-38 will be derived from plasma concentrations by noncompartmental analysis using actual times. Minimally, the following PK parameters will be calculated: maximum observed plasma concentration (C_{max}), time of maximum observed concentration following drug administration (t_{max}), area under the concentration-time curve (AUC). The Phase 2 PK data will be assessed using a PopPK approach, with the addition of Phase 1 data.

In Phase 1 the PK of both drugs (eribulin and irinotecan) will be assessed on C1D1 and in Phase 2 eribulin will be assessed on C1D1 and C1D8.

Pharmacokinetic and Pharmacodynamic Analyses

Exploratory/graphical analysis will be conducted for PK/ pharmacodynamic (PD) evaluations, ie, dose and/or exposure effect relationships will be explored for the effects of eribulin mesilate on tumor responses as determined by RECIST 1.1 (CR, PR and SD), PFS and ORR, as well as AEs/dose reductions, and may be followed by model-based analysis. In addition the effects of eribulin mesylate administration on absolute neutrophil count (ANC) may be evaluated using a semi-physiological model for hematological toxicity. Further details will be documented separately in a population analysis plan (PAP).

Safety Analyses

The primary endpoint for Phase 1, ie, the incidence of DLTs during Cycle 1 will be summarized by dose cohort for the DES using frequency and percentage.

Additionally, toxicity in Phase 2 for the Safety Analysis Set will be monitored on an ongoing basis. If the number of AEs that would have qualified as DLTs on the Phase 1 portion exceeds 1/3, a meeting

with the investigators will be convened to determine if the dose should be lowered. The rule of one-third (1/3) will be applied to the number of subjects in an increment of 3 subjects at the same dose level (eg, 3, 6, 9 subjects). Likewise, if ongoing moderate toxicities develop into “intolerable Grade 2” events, the recommended Phase 2 dose may also be re-evaluated in consultation with the protocol investigators.

All evaluation of safety other than the Phase 1 primary objective in DLT evaluation will be performed on the Safety Analysis Set. Safety data that will be evaluated include adverse events, clinical laboratory results, physical examination results, ECG, and vital signs.

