Subjects <12 months will be enrolled on to Schedule A only and at 1 dose level behind \geq 12 months subjects in order to maximize safety for infant subjects. These subjects are included for descriptive purposes only and will not contribute to the determination of the MTD/RP2D for this study, or to the sample size.

Dose Escalation

The traditional 3+3 design will be used for the conduct of Phase 1 of this study.

For both schedules A and B, 3 subjects will be entered into each dose level. The first subject at each dose level must complete the Day 8 assessments before further subjects can be entered at the same dose level. All 3 subjects in the cohort will be followed for a full cycle before the next dose level opens. If 1 subject experiences a DLT, the cohort will need to be expanded to 6 subjects on the same dose level.

If no DLT is observed in a dose cohort, then the dose can be escalated and 3 subjects can be enrolled onto the next dose level. The MTD is defined as the highest dose level at which fewer than 1/3 of subjects experience a DLT during Cycle 1 of therapy.

If, at dose level 0, there are 2 or more subjects with a DLT out of 3 subjects (or 2 DLTs out of 6 subjects after expansion) in Cycle 1, the MTD will have been exceeded and the dose will be deescalated to dose level -1, and the next 3 subjects will be enrolled onto this lower dose level.

The MTD will be determined based on the incidence of DLTs in Cycle 1 of each dose level. Subjects who do not complete Cycle 1 for any reason other than toxicity, ie, DLT, will be

replaced in that cohort in order to complete the number necessary (up to 6) to assess the safety of the dose level cohort.

Toxicities subsequent to Cycle 1 will also be reviewed, but will not count towards determination of dose escalation and MTD/RP2D. If protocol-defined DLTs are observed in a subject after the first cycle at any dose level, the dose will be reduced to the next lower dose level for subsequent cycles.

DLTs are defined as any of the following using the National Cancer Institute Common Terminology Criteria for Adverse Events (CTCAE Version 5.0) during Cycle 1:

Hematological:

1. Neutropenia Grade 4 that lasts >7 days
2. Thrombocytopenia Grade 4 on 2 separate days, or requiring a platelet transfusion on 2 separate days, within a 7-day period
3. Thrombocytopenia Grade 3 complicated by bleeding or requiring platelet or blood transfusion

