5.6.2 Dose Limiting Toxicities

The primary objective for phase 1 is to determine MTD and RP2D. The MTD is defined as the highest dose level at which less than 1/3 of subjects experience a DLT during Cycle 1 of therapy. The MTD will be determined based on the incidence of DLTs in Cycle 1 of each dose level.

MTDs will be obtained for both Schedule A and Schedule B and the most appropriate schedule will be taken forward to Phase 2 and will represent the RP2D (See Section 9.4.1 in the protocol for details on schedule selection).

The primary endpoint for Phase 1, ie, the incidence of DLTs will be summarized by dose level for the Dose Evaluable Set (DES) using frequency and percentage.

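### The Phase 2 toxicity trigger is one subject looser than the Phase 1 boundary from 6 subjects on, so 2 of 6 or 3 of 9 requires no dose-review meeting

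*Protocol*

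**What the plan says.** **Phase 2 trigger.** Protocol 9.7.1.8 has Phase 2 toxicity in the Safety Analysis Set watched continuously. The condition is "If the number of AEs that would have qualified as DLTs on the Phase 1 portion exceeds 1/3", and the consequence is that "a meeting with the investigators will be convened to determine if the dose should be lowered". The timing is given next: "The rule of one-third (1/3) will be applied to the number of subjects in an increment of 3 subjects at the same dose level", with 3, 6 and 9 as examples. The Safety Analyses part of the synopsis carries the same trigger ("If the number of AEs that would have qualified as DLTs on the Phase 1 portion exceeds 1/3, a meeting"). The SAP does not restate or alter it.

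**Phase 1 boundary.** Protocol 9.4.1 states: "The MTD is defined as the highest dose level at which fewer than 1/3 of subjects experience a DLT during Cycle 1 of therapy". SAP 5.6.2 agrees: "The MTD is defined as the highest dose level at which less than 1/3 of subjects experience a DLT during Cycle 1"; so does SAP 3.2.1. At dose level 0 the protocol also gives the count: with 2 of 3, "or 2 DLTs out of 6 subjects after expansion) in Cycle 1, the MTD will have been exceeded". After de-escalation to dose level -1, the synopsis says that if "2 DLTs are observed, that dose and schedule will be declared too toxic for further evaluation".

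**Other Phase 2 safeguards.** The same paragraph of 9.7.1.8 allows the dose to be reconsidered for intolerable Grade 2 toxicity, without a number. Protocol 9.7.3 and SAP section 6 add a tolerability assessment at the 9-subject futility analysis of each histology, also without a number. Withholding, reduction and discontinuation rules for the individual child are in 9.4.1.

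**The concern.** The Phase 2 rule takes over the Phase 1 DLT criteria and the one-third limit but puts the limit on the other side of the tie. Phase 1 tolerates only results below one-third; Phase 2 reacts only to results above it. Every check falls at a multiple of 3, so the tie is always attainable. The same count that forces de-escalation from dose level 0 in Phase 1 does not force even a discussion in Phase 2, and neither document gives a reason.

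At stake is whether a dose-review meeting is mandatory. This is the only numeric cohort-level trigger for reviewing the Phase 2 dose, in a paediatric population. The Phase 1 MTD determination and the ORR test do not depend on it.

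**Working it through.** **1. The plan's own boundary.** Below one-third at n = 6 means 3k < 6, so k is at most 1 and k = 2 fails. This reproduces the 2-of-6 statement in Protocol 9.4.1. No assumption is needed.

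**2. The two rules side by side**, with k the number of affected subjects among n. As written, a meeting needs 3k > n. Matched to Phase 1, it needs k ≥ 2 at n = 3 (1 of 3 only leads to expansion in Phase 1) and 3k ≥ n from n = 6.

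| n | As written | Matched |
|---|---|---|
| 3 | 2 | 2 |
| 6 | 3 | 2 |
| 9 | 4 | 3 |
| 12 | 5 | 4 |

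The rules agree at 3 subjects and differ by one subject afterwards. At 6 subjects the matched boundary is stated in Phase 1. Beyond 6 it is inferred from the MTD definition.

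**3. How often it matters.** The true rate p is assumed, because the documents give none. Subjects are independent and each counts once. Looks are at 3, 6, 9 and so on, and the probabilities are exact and cumulative over looks.

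By hand at p = 1/3, the probabilities of 0, 1, 2 or 3 affected among three subjects are 8/27, 12/27, 6/27 and 1/27.

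- By 3 subjects, either rule: 7/27 = 189/729 = 0.259.
- Added at 6 as written (total of 3 or more): (8/27)(1/27) + (12/27)(7/27) = 92/729. Cumulative: 281/729 = 0.385.
- Added at 6 matched (total of 2 or more): (8/27)(7/27) + (12/27)(19/27) = 284/729. Cumulative: 473/729 = 0.649.

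Continuing the same recursion (each cell is as written / matched):

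| True rate | By 6 | By 9 | By 24 |
|---|---|---|---|
| 10% | 0.036 / 0.114 | 0.038 / 0.125 | 0.040 / 0.130 |
| 20% | 0.148 / 0.345 | 0.172 / 0.388 | 0.209 / 0.436 |
| 25% | 0.229 / 0.466 | 0.271 / 0.524 | 0.355 / 0.606 |
| 30% | 0.321 / 0.580 | 0.385 / 0.648 | 0.525 / 0.754 |
| 1/3 | 0.385 / 0.649 | 0.463 / 0.720 | 0.637 / 0.832 |
| 40% | 0.518 / 0.767 | 0.617 / 0.835 | 0.824 / 0.935 |

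By 75 subjects at 40% the figures are 0.959 and 0.986.

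**4. How much rests on the boundary Phase 1 states itself.** Changing only the 6-subject look gives 0.659 by 9 subjects at 1/3 and 0.779 at 40%. The shares of the full gain are (0.659 − 0.463)/(0.720 − 0.463) = 76% and (0.779 − 0.617)/(0.835 − 0.617) = 74%.

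**5. Literal AE count.** If the numerator is events and a share of affected children have two, the rule as written fires by 9 subjects at p = 1/3 with probability 0.630 (share 25%) or 0.747 (share 50%). The matched subject count gives 0.720.

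**The case against.** A reader might infer that 2 of 6 in Phase 2 shows the recommended dose to have failed the trial's MTD definition. The documents do not support that. The MTD is determined in the Phase 1 Dose Evaluable Set (Protocol 9.7.1.2), and Dose Level 1 was carried forward after Phase 1 with a safety profile judged tolerable. The DLT counts are not given. If Dose Level 1 had 0 of 3 or 1 of 6 (an assumption), adding a Phase 2 result of 2 of 6 gives 2/9 = 22% or 3/12 = 25%. Adding 3 of 9 gives 3/12 = 25% or 4/15 = 27%. All are below one-third. The explicit 2-of-6 sentence also concerns dose level 0, a starting dose. A looser review trigger for a dose that has already passed is a defensible choice. That stands: this is a mismatch of boundaries, not proof of an intolerable dose.

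Nor do the documents support reading the gap as leaving children unprotected. Individual dose rules, the intolerable Grade 2 clause and the 9-subject tolerability assessment remain, and nothing bars a voluntary meeting at 2 of 6. But none of these supplies a number at exactly one-third.

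Two further points stand. The shortfall belongs to the subject-count reading: the trigger sentence counts AEs, and on that reading most or all of it goes. The following sentence, on applying the rule to subjects, makes the subject count the likelier intent, and the ambiguity is itself worth removing. The shortfall also narrows as subjects accrue at one dose level, so the main effect is a later meeting. Against this, the matched rule calls more meetings at rates most would accept.

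**Conclusion.** The point holds as a minor one that is cheap to correct. Counting subjects, the Phase 2 trigger is one subject looser than the Phase 1 boundary at every look from 6 on, and exactly one-third prompts no required meeting. That part needs no assumption.

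The size depends on assumed rates, independent subjects and one count per child. By 9 subjects the chance of a meeting is lower by 0.720 − 0.463 = 0.257 at a true rate of 1/3, and by 0.835 − 0.617 = 0.218 at 40%. By 75 subjects at 40% the difference is 0.986 − 0.959 = 0.027. The consequence is confined to whether, and how soon, a discussion is compulsory.

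**What to change.** In Protocol 9.7.1.8 and the synopsis, replace the trigger with:

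> A meeting will be convened if 2 or more of the first 3 subjects, or at least one-third of subjects at 6, 9, 12, ... treated at the same dose level, have at least one event meeting the DLT criteria of Section 9.4.1.

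This keeps the first look unchanged. A blanket rule of one-third or more would fire at 1 of 3, which has probability 0.488 at a true rate of 20% and is not an MTD breach in Phase 1. It also settles that subjects are counted.

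Do not add a Cycle 1 restriction. The Phase 2 monitoring is ongoing and the trigger states no cycle limit, so a restriction could drop later-cycle events from the only numeric trigger. Because the DLT list in 9.4.1 is introduced with reference to Cycle 1, the sponsor may want to say outright that events in any cycle count.

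**Cost.** One sentence in two places, and more meetings at rates below one-third. By 9 subjects the chance rises from 0.038 to 0.125 at 10%, from 0.172 to 0.388 at 20% and from 0.271 to 0.524 at 25%. Each is a discussion only: the trigger neither changes the dose nor halts accrual. If the sponsor prefers the present boundary to limit false alarms, it should say so and give the reason for departing from Phase 1.
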